Primary Endpoint	The primary effectiveness endpoint is the adjusted mean group difference in the HDRS-17 scores at 10 weeks compared to baseline for subjects in the Active device and the Sham device groups.			
Secondary Endpoints	 Arm difference in HDRS-17 response and remission rate at week 10. Arm difference in MADRS average score change, and response and remission rate at week 10. Arm difference in MADRS-s average score change, and response and remission rate at week 10. Arm difference in MADRS-s average score change, and response and remission rate at week 10. Quality of life improvement as measured by EQ-5D-3L in the active compared to sham arm at week 10. 			
Exploratory Endpoints	 Young Mania Rating Scale (YMRS) at 10 weeks. tDCS Adverse Events Questionnaire (AEQ) at 10 and 20 weeks Hamilton Anxiety Rating Scale (HAM-A) change at week 10. HDRS-17, MADRS, MADRS-s mean decrease, and remission and response rate at 20 weeks (after open-label) compared to open-label start and baseline. Correlation between MADRS and MADRS-s. Correlation between adherence to stimulation and HDRS-17/MADRS decrease in the active group at 10 weeks. Neuropsychological measure: verbal learning (Rey Auditory Verbal Learning Test (RAVLT) and information processing speed (Symbol-Digit Modalities Test (SDMT) Treatment acceptability questionnaire (TAQ) as developed by UEL. There is one form at baseline and another at week 10 and 20. The within-patient clinically meaningful improvement as defined as at least -3 points on the HDRS-17 scale. The percentage of subjects for each arm that 			

	reaches -3 points or more improvement and also the Cumulative Distribution Function Curves of Change in HDRS-17 Score from Baseline to Primary end-point
	by arm.
	by ann.
STATISTICAL CONSIDERATIO	NS
Sample Size	270
Statistical Plan	A modified intent to treat will be used. Users who have performed less than 10 sessions (300 minutes) during the first 3 weeks will be excluded from the analysis.
STUDY MANAGEMENT	
Principal Investigator UK	Professor of Affective Neuroscience [name], PhD, University East London
Principal Investigator US	Associate Professor of Psychiatry [name], PhD, University of Texas
Clinical Research Organization (CRO)	Curebase, Inc.

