7 SCHEDULE OF PROCEDURES

Table 1. Schedule of Procedures. Activities in blue cells are performed by trained graduate researchers supervised by a trained psychiatrist, and red cells are to be completed by the participant.

	Pre-Treatme nt		E	Blinded Pha	ise		Open-La Phas	abel e	Early termination ⁸
Activity	Week -3 to -1 (± 3 days)	Week 0	Week 1 (± 3 days)	Week 4 (± 3 days)	Week 7 (± 3 days)	Week 10 (± 3 days) Final blinded visit ¹	Week 10 (± 3 days) Open Label Start	Wee k 20 (± 3 days)	Week 1-20
Informed Consent	х								
Screening and baseline Video Call	х								
Diagnostic Assessment for MDD	X٩								
Intervention Kit Shipped to subject	X ⁵								
Randomization ⁶		Х							
Technical onboarding		х							
Initial Visit		Х							
Video call	Х	Х	Х	Х	Х	Х		Х	Х
MINI	Х								
HDRS-17	X		X	Х	X	X		X	X
MADRS	Х		Х	Х	Х	Х		X	Х
MADRS-s	X	X ⁴	X	X	X	X		X	Х
C-SSRS	X		X X	X X	X X	X		X	X X
YMRS	X X		X	X	X	X X		X	X
HAM-A	X					X		X X	X
EQ-5D-3L RAVLT	X					X		X	X
SDMT	~	X ²				 X ²		Λ X ²	^
TAQ	X	~				X		X	Х
AEQ						X		X	X
Healthcare Visit Survey ³						X		X	X
FLOW FL-100 use ⁷		х	х	х	х	х	х	Х	
Record/Review Concomitant Medications	х	х	х	х	х	х		х	х
Record/Review Adverse Events		Х	Х	Х	Х	Х		Х	Х

CA-127-T1, v3.0 Flow Neuroscience AB, FL001 CONFIDENTIAL Page **19** of **69**

¹ The week 10 visit includes the study Primary end-point. This will be the final blinded visit and will be the start of the open label phase of the study. Participants in the Sham arm will be informed of their assignment and will restart with active stimulation for 10 weeks; participants in the Flow FL-100 arm will be allowed to continue maintenance treatment for 10 more weeks at 3 sessions per week. The unblinding will occur after the primary end-point data has been recorded. ² Optional

³ Participants will be surveyed about the number of times he/she has sought healthcare due to depression during the previous 10 weeks.

⁴ Participants will be required to answer the nine questions of the MADRS-s form in the app to start the first stimulation session during the technical onboarding.

⁵ Participants will be required to start treatment within 24 days from completing the baseline surveys.

⁶ Completed after eligibility is confirmed by the investigator; when the participant signs up with their email in the trial app they will automatically be randomized to the sham or active treatment arm (with 50% probability).

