22.3.3 MODIFIED INTENT-TO-TREAT ANALYSIS SET (MITT)

The modified intent-to-treat (mITT) analysis set will include ITT subjects who receive at least 1 treatment of study device (Active or Sham) and will exclude patients who were randomized in error. The number of exclusions from the mITT analysis set is expected to be small and will only be

based on information that was known or could have been known prior to the first treatment. Subjects in the mITT population will be analyzed in the group to which they were randomized.

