22.3.4 PER PROTOCOL ANALYSIS SET (PP)

The Per Protocol (PP) analysis set will be comprised of the following:

- Subjects in the mITT analysis set
- Subjects with device failure within the 10-week follow-up period
- Subjects with deviation from the clinical investigation plan is caused by the investigational device or by problems with respect to tolerability

Subjects who will be excluded from the PP analysis set are as follows:

- Subjects with major protocol violations that would be expected to confound clinical assessment during follow-up as determined by the PIs.
- Subjects who took new pharmaceutical substances or treatments during the clinical investigation which are listed as an exclusion criteria;
- Subjects who do not meet the inclusion criteria or exclusion criteria.
- Users who have performed less than 10 sessions (300 minutes) during the first 3 weeks will be excluded from the analysis.

Subjects in the PP population will be analyzed in the group to which they were randomized.

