22.5 TESTING OF PRIMARY EFFECTIVENESS HYPOTHESES

The primary effectiveness endpoint is the change in adjusted mean group difference in the HDRS-17 scores between 10 weeks and baseline between subjects randomized to the active study device relative to those subjects randomized to sham. The formal statistical hypothesis is as follows:

$$H_{o}: d_{flow} - d_{sham} \leq 0 \\ H_{a}: d_{flow} - d_{sham} > 0$$

Where d_{flow} and d_{sham} are the adjusted mean group difference in HDRS-17 scores in subjects randomized to Active and Sham groups, respectively.

The mITT population will be the analysis population used to analyze the primary effectiveness endpoint. The endpoint will be analyzed when all randomized subjects have completed their 10-week visit, been withdrawn

from the trial or passed the end of their 10-week follow-up visit window. The difference in the group mean differences will be assessed using a mixed model for repeated measures. If the p-value of the difference in the group mean differences is less than one-sided p= 0.025, then the trial declared a success.

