22.9 EXPLORATORY ENDPOINTS

The following list of secondary endpoints will be analyzed using the mITT population and will be summarized based on the type of data: Continuous (CONT), Binary (BIN) or Correlation (CORR):

- Montgomery–Åsberg Depression Rating Scale (MADRS) response rate at all follow-up time points (CONT)
- Montgomery–Åsberg Depression Rating Scale Self-report (MADRS-s) scores of the two arms (response and remission rates) at all time points (CONT)
- Hamilton Anxiety Rating Scale (HAM-A) at all time points (CONT)
- Young Mania Rating Scale (YMRS) at all time points (CONT)
- tDCS Adverse Events Questionnaire (AEQ) at 10 and 20 weeks (CONT)
- HDRS-17 (CONT), MADRS (CONT), MADRS-s mean decrease (CONT), remission (BIN), and response rate (BIN) at 6 weeks comparison between groups.
- HDRS-17 (CONT), MADRS (CONT), MADRS-s (CONT) at 20 weeks (after open-label)
- Correlation between MADRS and MADRS-s. (CORR)
- Correlation between the percent of sessions using the FLOW FL-100 and HDRS-17/MADRS decrease in the active group at 10 weeks.
- The within-patient clinically meaningful improvement as defined as at least -3 points on the HDRS-17 scale. The percentage of subjects for each arm that reaches -3 points or more improvement and also the Cumulative Distribution Function Curves of Change in HDRS-17 Score from Baseline to Primary end-point by arm.

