22.15 INTERIM ANALYSES

An interim analysis testing for futility, sample size re-estimation, and claiming study success with a sample size smaller than the maximum specified is specified. Please see the details in the Adaptive Design Report detailing all elements of this process.

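### The Study Summary excludes participants with fewer than 10 early sessions from the mITT analysis; section 22 keeps them in the primary population and makes that rule per-protocol only

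*Protocol*

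**What the plan says.** Four places in the protocol bear on who enters the primary analysis.

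- **Section 6, Study Summary, Statistical Plan.** "A modified intent to treat will be used. Users who have performed less than 10 sessions (300 minutes) during the first 3 weeks" are to be left out of the analysis. This is the only statement about an analysis population in the Study Summary.
- **Section 22.3.3, mITT.** "The modified intent-to-treat (mITT) analysis set will include ITT subjects who receive at least 1 treatment of study device (Active or Sham"). Participants randomised in error are removed. The section limits exclusions to those "based on information that was known or could have been known prior to the first treatment", and participants are analysed in the arm to which they were randomised.
- **Section 22.3.4, per protocol.** Among the exclusions from this set: "Users who have performed less than 10 sessions (300 minutes) during the first 3 weeks will be excluded from the analysis".
- **Section 22.5, primary test.** "The mITT population will be the analysis population used to analyze the primary effectiveness endpoint".

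Section 22.9 relies on the same set: "The following list of secondary endpoints will be analyzed using the mITT population".

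**The concern.** The Study Summary attaches to the mITT analysis an exclusion that section 22.3.3 does not contain and that its own limit forbids, since a session count over the first three weeks cannot be known before the first session. The wording matches the per-protocol exclusion in 22.3.4, so the two sets appear to have been merged in the summary.

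What is at stake is the comparison as randomised. Session count is observed after randomisation and may depend on treatment, on tolerability and on how the participant is doing. The protocol itself allows for a link with outcome: sections 11.7 and 22.9 plan to correlate session use with the fall in HDRS-17 and MADRS in the active arm. Dropping low users would turn the primary analysis into an adherence-selected one. Because 22.9 also uses the mITT set, the ambiguity reaches the endpoints listed there.

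**Working it through.** **1. The texts side by side.** Classifying a participant by sessions in weeks 1 to 3, and considering session count alone:

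| Sessions, weeks 1-3 | Study Summary | mITT (22.3.3), primary under 22.5 | Per protocol (22.3.4) |
|---|---|---|---|
| 0, and never treated later | out | out | out |
| 1 to 9 | **out** | **in** | out |
| 10 to 15 | in | in | in |

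The Study Summary column agrees with the per-protocol column and disagrees with the mITT column. The conflict is confined to treated participants with 1 to 9 early sessions.

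**2. Can such participants be completers?** Section 7 schedules 5 x 3 = 15 sessions in weeks 1 to 3 and 3 x 7 = 21 in weeks 4 to 10, 36 in all. The threshold of 10 is 10/15 = 66.7% of the early schedule. Section 15.4 withdraws participants who cannot reach 22 of 36 sessions. With x early sessions, 22 - x of the remaining 21 are needed:

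- x = 9: 13 of 21 (61.9%).
- x = 1: 21 of 21 (100%).

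So every count from 1 to 9 is compatible with reaching 22, and the withdrawal rule does not dispose of the conflict. Sections 15.3 and 15.6 give indirect support for keeping such people in: participants who miss Week 10 enter the primary analysis by multiple imputation, and data already collected from withdrawn participants are used. Neither section mentions session counts, and the contradiction does not depend on them.

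**3. The planned effect, as a yardstick.** Section 22.2 uses a difference of 3.2, standard deviations of 7.1 and 7.9, and one-sided alpha 0.025. The pooled SD is sqrt((7.1² + 7.9²)/2) = 7.511. With the noncentral t distribution, 88 per arm gives 80.2% power and 108 per arm gives 87.6%; 216/(1 - 0.20) = 270. The stated 176, 87.6% and 270 reproduce. Nothing in this point turns on them; 3.2 serves only as a scale.

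**4. How far the estimate could move.** In one arm, let f be the fraction excluded and g the mean improvement of retained minus excluded participants. The full-arm mean equals the retained mean minus f x g, so exclusion raises the arm mean by f x g. The treatment difference therefore shifts by

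shift = f_active x g_active - f_sham x g_sham.

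The protocol gives neither f nor g. Purely as an assumption, take f from 0 to 0.15 and g from 0 to 6 HDRS-17 points in each arm:

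- minimum: 0 - 0.15 x 6 = -0.9
- maximum: 0.15 x 6 - 0 = +0.9
- zero whenever the two products are equal

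0.9/3.2 = 28% of the planned difference. This range presumes that low users never do better than the others. If g may run from -6 to +6, for instance because some stop early feeling well, the extremes become 0.15 x 6 + 0.15 x 6 = 1.8 in either direction (1.8/3.2 = 56%).

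**The case against.** The strongest reply is that the primary population is not really in doubt. The Study Summary entry never uses the word primary and does not define mITT. Only 22.3.3 defines the set, only 22.5 assigns it to the primary endpoint, and those sections agree. On this reading the summary line is a drafting slip that section 22 corrects, and the SAP, which was not available for this check, may restate the population. It can be added that participants are blinded and that section 9.1 cites equal tolerability and dropout across arms in the literature, so any bias may be nil.

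Part of this stands. Section 22 is the more explicit text, and a slip is the likeliest explanation. The range in the working rests on assumed inputs and should not be quoted as an estimate.

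The rest does not remove the point. The summary names the very set that 22.5 makes primary, and the protocol gives no order of precedence. A correct SAP would leave the protocol contradicting itself. Published dropout rates say nothing about session counts in this trial or the outcomes of low users, and blinding does not guarantee equal adherence.

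**Conclusion.** The contradiction is certain on the face of the protocol and should be corrected. It concerns which randomised participants enter the primary test, and it affects treated participants with 1 to 9 sessions in the first three weeks. The Study Summary rule is the one that fails, judged against 22.3.3's own limit on exclusions and its agreement with 22.5; that the sponsor intended section 22 is an inference from this.

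The numerical consequence is unknown in size and direction. It is zero if low use and its relation to outcome are alike in both arms, and the figures of 0.9 and 1.8 points hold only under the assumptions stated with them. No effect on type I error or power is claimed.

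**What to change.** Replace the Statistical Plan entry in the Study Summary with the 22.3.3 definition: randomised participants who had at least one treatment, analysed as randomised, excluding only those randomised in error. Keep the 10-session rule solely as a per-protocol exclusion in 22.3.4. Sections 22.3 and 22.5 need no change.

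Make the correction before any comparative data are examined, including at the interim analysis. Unblinding is not a usable deadline. Participants are told their arm one at a time, each after their own Week 10 visit (section 7, footnote 1: "The unblinding will occur after the primary end-point data has been recorded"), and section 22.15 allows the interim analysis to end in "claiming study success with a sample size smaller than the maximum specified".

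The cost is one entry. Low users stay in the primary analysis, so the estimate may be less favourable than under the Study Summary rule if they improve less on active treatment. The per-protocol analysis will still show the result without them.

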7 SCHEDULE OF PROCEDURES

Table 1. Schedule of Procedures. Activities in blue cells are performed by trained graduate researchers supervised by a trained psychiatrist, and red cells are to be completed by the participant.

	Pre-Treatme nt		E	Blinded Pha	ise		Open-La Phas	abel e	Early termination ⁸
Activity	Week -3 to -1 (± 3 days)	Week 0	Week 1 (± 3 days)	Week 4 (± 3 days)	Week 7 (± 3 days)	Week 10 (± 3 days) Final blinded visit ¹	Week 10 (± 3 days) Open Label Start	Wee k 20 (± 3 days)	Week 1-20
Informed Consent	х								
Screening and baseline Video Call	х								
Diagnostic Assessment for MDD	X٩								
Intervention Kit Shipped to subject	X ⁵								
Randomization ⁶		Х							
Technical onboarding		х							
Initial Visit		Х							
Video call	Х	Х	Х	Х	Х	Х		Х	Х
MINI	Х								
HDRS-17	X		X	Х	X	X		X	X
MADRS	Х		Х	Х	Х	Х		X	Х
MADRS-s	X	X ⁴	X	X	X	X		X	Х
C-SSRS	X		X X	X X	X X	X		X	X X
YMRS	X X		X	X	X	X X		X	X
HAM-A	X					X		X X	X
EQ-5D-3L RAVLT	X					X		X	X
SDMT	~	X ²				 X ²		Λ X ²	^
TAQ	X	~				X		X	Х
AEQ						X		X	X
Healthcare Visit Survey ³						X		X	X
FLOW FL-100 use ⁷		х	х	х	х	х	х	Х	
Record/Review Concomitant Medications	х	х	х	х	х	х		х	х
Record/Review Adverse Events		Х	Х	Х	Х	Х		Х	Х

CA-127-T1, v3.0 Flow Neuroscience AB, FL001 CONFIDENTIAL Page **19** of **69**

¹ The week 10 visit includes the study Primary end-point. This will be the final blinded visit and will be the start of the open label phase of the study. Participants in the Sham arm will be informed of their assignment and will restart with active stimulation for 10 weeks; participants in the Flow FL-100 arm will be allowed to continue maintenance treatment for 10 more weeks at 3 sessions per week. The unblinding will occur after the primary end-point data has been recorded. ² Optional

³ Participants will be surveyed about the number of times he/she has sought healthcare due to depression during the previous 10 weeks.

⁴ Participants will be required to answer the nine questions of the MADRS-s form in the app to start the first stimulation session during the technical onboarding.

⁵ Participants will be required to start treatment within 24 days from completing the baseline surveys.

⁶ Completed after eligibility is confirmed by the investigator; when the participant signs up with their email in the trial app they will automatically be randomized to the sham or active treatment arm (with 50% probability).

⁷ Five sessions per week for 3 weeks, followed by three sessions per week for 7 weeks. In total, thirty-six sessions during 10 weeks during the blinded phase. Please refer to Table 2 and Table 3 below for more details.

⁸ In case there is an early termination the research staff can request to have an early termination interview, if the subject agrees.

⁹ Diagnostic Assessment for MDD will be performed by Investigator-Psychiatrist according to the most recent APA Practice Guideline for treatment of MDD.

	1011011 301	icuule uulli	ig billiaca	pridoc.						
Week	1	2	3	4	5	6	7	8	9	10
Number of sessions	5	5	5	3	3	3	3	3	3	3

Table 2. Stimulation schedule during blinded phase.

Table 3. Stimulation schedule during open-label phase.

Week	Previous assignm ent	1	2	3	4	5	6	7	8	9	10
Number of	Active	3	3	3	3	3	3	3	3	3	3
sessions	Sham	5	5	5	3	3	3	3	3	3	3

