11.4 OPEN LABEL PHASE

After the completion of the blinded treatment phase all participants will be offered to continue the treatment. Members of the sham group will be offered to restart the treatment with active stimulation, while members of the active group will be offered to continue maintenance treatment for 10 more weeks at 3 sessions per week.

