11.5 PRIMARY ENDPOINTS

The primary effectiveness endpoint is the adjusted mean group difference in the HDRS-17 scores at 10 weeks compared to baseline for subjects in the Active device and the Sham device groups.

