11.6 SECONDARY ENDPOINTS

- Arm difference in HDRS-17 response and remission rate at week 10.
- Arm difference in MADRS average score change, and response and remission rate at week 10.
- Arm difference in MADRS-s average score change, and response and remission rate at week 10.
- Quality of life improvement as measured by EQ-5D-3L in the active compared to sham arm at week 10.

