13.2 WEEK 0

To allow the Investigator's assessment of the participant's progress, the participant will complete a video call with study staff and undergo the following:

- Review of concomitant medications
- Record any new or updated adverse events and device deficiencies, if applicable
- SDMT baseline
- Technical onboarding & device training session
- Randomization

13.3 WEEKS 1, 4 & 7

To allow the Investigator's assessment of the participant's progress, the participant will complete a video call with study staff and undergo the following:

- ClinROs
 - HDRS-17

- MADRS
- YMRS
- C-SSRS
- Review of concomitant medications
- Record any new or updated adverse events and device deficiencies, if applicable

13.4 WEEK 10

To allow the Investigator's assessment of the participant's progress, the participant will complete a video call with study staff and undergo the following:

- ClinROs/PROs
 - HDRS-17
 - MADRS
 - HAM-A
 - YMRS
 - EQ-5D-3L
 - RAVLT
 - SDMT
 - TAQ
 - AEQ
 - C-SSRS
- Review of concomitant medications
- Record any new or updated adverse events and device deficiencies, if applicable

For participants in the Sham Arm:

• Participants in the Sham arm will be informed of their assignment and will be offered to start active, Open-Label stimulation for 10 weeks, with 5 sessions the first 3 weeks and then up to 3 sessions per week.

For participants in the Active stimulation Arm:

- Participants in the Active arm will be offered to continue maintenance treatment for 10 more weeks at 3 sessions per week.
- 13.5 WEEK 20 FOLLOW-UP VISIT OPEN-LABEL ONLY

To allow the Investigator's assessment of the participant's progress, the participant will complete a video call with study staff and undergo the following:

- ClinROs/PROs
 - HDRS-17
 - MADRS
 - HAM-A
 - YMRS
 - EQ-5D-3L
 - RAVLT
 - SDMT
 - TAQ
 - AEQ
 - C-SSRS
- Review of concomitant medications
- Record any new or updated adverse events and device deficiencies, if applicable.

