22.11 EVALUATION OF BLINDING

An evaluation of blinding will be performed. Prior to subjects unblinding through the system they will respond to the question "Which treatment arm do you think you are in?" (answers: sham/active), followed by the question "How certain are you of this?", with the options 1 to 5 where 5 is very certain and 1 is very uncertain. The counts and percentages of the subjects responding correctly will be tabulated and reported.

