24.2 CAPTURE OF PATIENT REPORTED OUTCOMES

Patient reported outcomes (PROs) will be collected via the participant's personal smartphone or other device running Android 5.0+ or iOS 12+ and the data will be transmitted directly into the EDC. As the data is originated in the participant's device, it is considered to be electronic source and the data is automatically locked as soon as it enters the EDC to ensure that it is secure.

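### Unblinding at Week 10 is tied only to recording of the primary endpoint, which does not secure blinded completion of the participant self-reports

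*Protocol*

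**What the plan says.** Table 1, footnote 1 (Section 7) says of the Week 10 visit: "This will be the final blinded visit and will be the start of the open label phase of the study". It then gives the rule for disclosure: "The unblinding will occur after the primary end-point data has been recorded".

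Section 11.5 defines the endpoint in question: "The primary effectiveness endpoint is the adjusted mean group difference in the HDRS-17 scores at 10 weeks compared to baseline". No other instrument is part of it.

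Section 13.4 lists the Week 10 assessments and then states, for those on sham: "Participants in the Sham arm will be informed of their assignment and will be offered to start active, Open-Label stimulation for 10 weeks". It sets no condition on the order of the two.

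One other step is expressly placed before disclosure, the blinding questionnaire in Section 22.11: "Prior to subjects unblinding through the system they will respond to the question".

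On capture, Section 24.2 says: "Patient reported outcomes (PROs) will be collected via the participant's personal smartphone". The study summary (Section 6) says the same of the MADRS-s at each scheduled week, including Week 10.

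Several of these Week 10 self-reports are compared between arms. MADRS-s change, response and remission are secondary endpoints in Section 11.6, as is this one: "Quality of life improvement as measured by EQ-5D-3L in the active compared to sham arm at week 10". Section 22.8 places EQ-5D-3L, and response with MADRS-s named in its definition, in the list of secondary endpoints under multiplicity control.

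**The concern.** A release rule for the blind should protect every outcome that is compared between arms at that visit. This one names only the primary endpoint. HDRS-17 is rated by staff on the video call, whereas the self-reports go in through the participant's own device. A site or system could therefore satisfy footnote 1 and the Section 22.11 questions, and disclose the arm, while one or more self-reports are still open.

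Participants who have just learned that they received sham or active stimulation may rate mood and quality of life differently for that reason, and the two arms would move apart. MADRS-s and EQ-5D-3L feed comparisons that the protocol tests after the primary succeeds. The AEQ is the instrument that Section 19 designates for the frequency and severity of anticipated adverse events. Table 1 schedules EQ-5D-3L and TAQ at only one blinded visit after baseline, and the AEQ at only one blinded visit, namely Week 10 in each case. A Week 10 answer given with the arm known therefore has no scheduled blinded substitute. MADRS-s does have readings at Weeks 1, 4 and 7, but its secondary endpoint is at Week 10.

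**Working it through.** The protocol gives no figure on this point, so the check is mainly a reading of the passages side by side.

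**1. What must happen before disclosure.**
- Primary endpoint data recorded: required (Table 1, footnote 1).
- Blinding questions answered: required (Section 22.11).
- MADRS-s, EQ-5D-3L, TAQ and AEQ submitted: required nowhere in the protocol.

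**2. What is scheduled at Week 10 and how it is captured.**

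| Instrument | Table 1, Week 10 | Section 13.4 list | Type (Section 14) |
|---|---|---|---|
| HDRS-17 | yes | yes | clinician |
| MADRS, HAM-A, YMRS, C-SSRS, RAVLT | yes | yes | clinician |
| EQ-5D-3L, TAQ, AEQ | yes | yes | self-report |
| MADRS-s | yes | no | self-report |

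The clinician scales belong to the same video call as HDRS-17, so disclosure between them is unlikely in practice. The self-reports depend on the participant completing a form. MADRS-s is the most exposed, because the visit procedure does not mention it at all.

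**3. Effect on the primary.** By the rule itself, HDRS-17 is recorded before disclosure, so the primary analysis is not affected. The sample size does not depend on this point either. With SD = √((7.1² + 7.9²)/2) = 7.51 and a difference of 3.2, a two-sample t-test at one-sided 0.025 needs 88 per arm, or 176. Power at 108 per arm is 87.6%, and 216/0.80 = 270, all as stated in Section 22.2.

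**4. Size.** Two quantities would be needed: f, the share of a given self-report completed after disclosure, and s, the shift in the between-arm difference (in SD) among those participants. The protocol gives neither, so no estimate is possible. For scale only, assume a continuous self-report, no true effect, 108 per arm (216/2), and a shift that favours active. The bias is f × s, and the nominal one-sided 0.025 error becomes Φ(f·s·√(108/2) − 1.96), with √54 = 7.35:

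| f (assumed) | s = 0.1 | s = 0.2 | s = 0.4 |
|---|---|---|---|
| 10% | 0.030 | 0.035 | 0.048 |
| 25% | 0.038 | 0.056 | 0.110 |
| 50% | 0.056 | 0.110 | 0.312 |

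For example, f = 25% and s = 0.2 give a bias of 0.05 SD and Φ(0.37 − 1.96) = 0.056. The table runs from trivial to serious according to inputs nobody can read from the protocol. It shows only that the matter is not harmless by construction. These are nominal rates for one test; the secondary tests are also gated on the primary and adjusted under Section 22.10.

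**The case against.** The case that the protocol already protects these outcomes is substantial.

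- Footnote 1 sets an earliest point. It does not say that disclosure follows at once or precedes the other forms.
- Table 1 has two Week 10 columns. Every assessment sits in the last blinded visit, and the open-label column carries only device use.
- Section 13.4 lists the assessments before the text on disclosure and presents EQ-5D-3L, TAQ and AEQ as part of the call. Section 11.4 adds: "After the completion of the blinded treatment phase all participants will be offered to continue the treatment".
- The protocol also uses primary end-point for the time point (the last exploratory endpoint in Section 11.7), so footnote 1 could be read as meaning all Week 10 data.
- Section 22.11 describes unblinding as a system step, and Section 12.6 keeps the raw allocation data from trial staff. An announcement by the rater in mid-call is not what is described.
- Section 24.2 gives the capture device, not a later time of completion.

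Most of this stands. It shows that the intent is blinded collection, and it lowers the risk for the clinician-rated scales. A reader might infer that the protocol plans to collect its secondary outcomes unblinded, or releases the blind part-way through the visit. The documents do not say that.

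What remains is that none of these passages makes completion of the self-reports a condition for disclosure. The order of a list is not a rule, and MADRS-s is not on that list. Section 11.4 speaks of the treatment phase, not of completed assessments. The broader reading of footnote 1 is possible, but a site is equally entitled to read it through Section 11.5.

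**Conclusion.** The release condition is incomplete. It protects HDRS-17 and, through the shared call, largely protects the clinician-rated scales. It does not secure blinding for MADRS-s, EQ-5D-3L, TAQ and AEQ at Week 10. The primary analysis is intact, so this is an inexpensive improvement to the protection of secondary and exploratory outcomes and does not threaten the trial's main conclusion.

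A reader might go further in two ways that the documents do not support. One is to state the bias as a fraction of the assumed treatment effect: both inputs would be assumptions, and the assumed effect belongs to HDRS-17, which is not exposed. The other is to say that the bias favours active throughout. That is plausible for mood and quality of life, but for the AEQ, knowing that one had active stimulation could as easily raise the reporting of side effects.

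The conclusion rests on the protocol alone. Operational documents not shown may already fix the order, in which case the protocol text should be brought into line with them.

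**What to change.** In Table 1 footnote 1 and in Section 13.4, state that the assignment is revealed only after all Week 10 clinician-rated and self-reported outcomes in Table 1, expressly including MADRS-s, and the Section 22.11 blinding questions have been recorded or marked not done. Add MADRS-s to the Section 13.4 list. Since Section 22.11 already routes unblinding through the system, have the system release the assignment on that check.

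Flag any Week 10 item first entered after disclosure and examine it in a sensitivity analysis. Outright exclusion is not advisable, because it could create missing data related to arm or outcome.

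The cost is a sentence in two places, one list entry and one system check. The downside is that disclosure waits until the participant has finished the forms; the option to mark an item not done keeps an unreturned form from holding it up indefinitely.
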